12.0 Provisions to Monitor the Data to Ensure the Safety of Subjects*

12.1 The plan to periodically evaluate the data collected regarding both harms and benefits to determine whether subjects remain safe is as follows:

- The principal investigator and statistician will review cumulative VAS Pain scores, RCS data, QuickDASH, number of digital ulcers, and number of attacks/episodes per week data at the halfway point (8 subjects).
- If any of the change in VAS Pain scores, RCS, QuickDASH, number of digital ulcers, or number of attacks/episodes per week for the treatment should become statistically significantly worse than the control with a $p < 0.05$ then the study will be suspended immediately.
- Alternatively, if the change in VAS Pain scores, RCS, QuickDASH, number of digital ulcers and number of attacks/episodes per week for the treatment should become statistically significantly better than the control with a $p < 0.05$ then the study will also be suspended immediately.

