8.0 Study Endpoints*

8.1 Primary endpoints: Participation in the study will end 12 months after the baseline visit or if the patient elects to be removed from the study, whichever comes first.

PROTOCOL TITLE: The Effect of Abobotulinum Toxin A on the Symptoms of Raynaud's Phenomenon, a Double-Blind Randomized Placebo-Controlled Trial

- 8.2 Primary and secondary safety endpoints: adverse reaction to the abobotulinum toxin A solution. If a participant develops a reaction, he or she will be given the option to withdraw but will not be required to withdraw, unless life threatening.

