9.2 Timeline

- Subject visits
 - The abobotulinum toxin A solution and saline solution will be prepared the same day as the subject's baseline visit
 - Baseline Visit
 - a. Minute 00-20:
 - i. Screening and consent process in screening room
 - b. Minute 20-40:
 - i. Assessment of baseline Raynaud's symptoms via Baseline Case Report (attached) and photographs will be taken of both hands
 - ii. Administration of abobotulinum toxin A solution and normal saline solution
 - c. Minute 40-60:
 - i. Review post-procedure instructions and how to complete Brief Follow-up Case Reports. Observe subject for any adverse reaction.
 - 48-hour follow-up phone call:

[figure not shown]
PROTOCOL TITLE: The Effect of Abobotulinum Toxin A on the Symptoms of Raynaud's Phenomenon, a Double-Blind Randomized Placebo-Controlled Trial

- a. Minute 0-5:
 - i. Brief phone call to assess for any adverse reactions.
- 1-month (+/- 8 days) Follow-up
 - a. Minute 00-15:
 - i. Assessment of Raynaud's symptoms via Follow-up Case Report (attached) and photographs will be taken of both hands
- 3-month (+/- 15 days) Follow-up
 - a. Minute 00-15:
 - i. Assessment of Raynaud's symptoms via Follow-up Case Report (attached)
- 6-month (+/- 15 days) Follow-up
 - a. Minute 00-15:
 - i. Assessment of Raynaud's symptoms via Follow-up Case Report (attached) and photographs will be taken of both hands
- 12-month (+/- 15 days) Follow-up
 - a. Minute 00-15:
 - i. Assessment of Raynaud's symptoms via Follow-up Case Report (attached) and photographs will be taken of both hands
- Subject surveys
 - Months 0-3:
 - a. Every week the subjects will be asked to complete the Brief Follow-up Case Report either online or on a paper version given to the subject.
 - Months 4-12
 - a. Every month the subjects will be asked to complete the Brief Follow-up Case Report either online or on a paper version given to the subject
- Solution preparation

PROTOCOL TITLE: The Effect of Abobotulinum Toxin A on the Symptoms of Raynaud's Phenomenon, a Double-Blind Randomized Placebo-Controlled Trial

- 300 unit vials of abobotulinum toxin A will be reconstituted with 10 ml of non-bacteriostatic normal saline yielding a final concentration of 30 units per 1 ml.
- The solutions will be drawn up in 1 cc syringes utilizing a 25g needle by [name]. The needle will then be replaced with a capped 30g ½ inch needle.

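### The halfway safety review omits adverse reactions, the protocol's own safety endpoint; a descriptive by-hand listing would close the gap

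*Combined protocol and SAP*

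**What the plan says.** Section 12.1 opens with its purpose: "The plan to periodically evaluate the data collected regarding both harms and benefits to determine whether subjects remain safe is as follows". What follows is one look, at 8 of the planned 16 subjects. The reviewers and the data are given as "The principal investigator and statistician will review cumulative VAS Pain scores, RCS data, QuickDASH, number of digital ulcers", plus weekly attacks. These five measures are the outcomes named in section 11.1.

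Two suspension rules follow, both at p < 0.05 against control. The harm rule begins "If any of the change in VAS Pain scores, RCS, QuickDASH, number of digital ulcers, or number of attacks/episodes per week". The benefit rule names the same five measures but joins them differently: "number of digital ulcers and number of attacks/episodes per week for the treatment should become statistically significantly better than the control".

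The safety endpoint is defined elsewhere. Section 8.2 reads "Primary and secondary safety endpoints: adverse reaction to the abobotulinum toxin A solution". Adverse reactions are gathered in several ways:
- observation during and after injection (sections 9.2 and 9.3);
- at 48 hours, a "Brief phone call to assess for any adverse reactions" (section 9.2);
- a clinic number for subjects to call, and an evaluation in person or by phone at 1 and 3 months (section 9.2);
- an Adverse Event Form among the source documents (section 9.3).

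Section 13.1 provides for withdrawal of a subject who becomes intolerant to treatment. Section 24.3 gives all investigators access to everything collected.

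**The concern.** A review that is meant to decide whether subjects remain safe should look at the endpoint that the protocol defines as safety. As written, section 12.1 could be followed to the letter without anyone tabulating adverse reactions across subjects or comparing treated with control hands. Each subject receives toxin in one hand and saline in the other, so that comparison is easily made. For a local effect such as the temporary muscle weakness listed in section 14.1, it is also the most informative one available.

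Two smaller matters sit in the same section. Both rules need the direction of treatment against control, and the principal investigator, who also discusses consent and eligibility with each subject (section 9.2), is a named reviewer in a trial described as double-blind. And the change from *any ... or* in the harm rule to *and* in the benefit rule leaves open whether benefit must be shown on all five outcomes.

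**Working it through.** **Timing of the look.** Section 11.2 gives d = 2/1.92 = 1.04 and 16 patients. A two-sided independent t-test at 0.05 with 16 hands per arm has power 0.812, so the stated 16 reproduces. The halfway look is 16/2 = 8 subjects, that is, 8 treated and 8 control hands.

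**Is the safety endpoint in any cumulative review?** Set the sections side by side. Section 12.1 lists five measures and no adverse events. Sections 8.2, 9.2, 9.3 and 13.1 collect or act on adverse reactions subject by subject. Section 24.3 gives access but prescribes no review. Collection and access are therefore present; a cumulative step is not.

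**Could QuickDASH stand in?** It is the listed measure closest to hand weakness. If it is one score per person, it gives no treated-versus-control comparison at all. If it is scored per hand (an assumption, since the forms are not in the documents), suppose k of 8 treated hands worsen by δ SD:
- Mean shift = kδ/8. For k = 3 and δ = 1 this is 0.375 SD.
- Independent t-test (section 11.1): expected signal about 0.375/√(2/8) = 0.75, against a critical value of 2.145 (14 df).
- Paired test at between-hand correlation 0.7: 0.375/√(2 × 0.3/8) = 1.37, against 2.365 (7 df).

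Both signals fall well short. Simulation (normal data, 200,000 runs per cell, two-sided 0.05) gives the share of trials significant in the worse direction. Columns show the assumed between-hand correlation.

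| Scenario | Test | 0 | 0.3 | 0.5 | 0.7 |
|---|---|---|---|---|---|
| 3 of 8, 1 SD | independent | 0.084 | 0.057 | 0.038 | 0.019 |
| 3 of 8, 1 SD | paired | 0.078 | 0.092 | 0.105 | 0.130 |
| 3 of 8, 2 SD | independent | 0.155 | 0.123 | 0.096 | 0.067 |
| 3 of 8, 2 SD | paired | 0.139 | 0.157 | 0.173 | 0.192 |
| 4 of 8, 1 SD | independent | 0.125 | 0.093 | 0.069 | 0.043 |
| 4 of 8, 1 SD | paired | 0.113 | 0.139 | 0.167 | 0.221 |

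For 3 of 8 at 1 SD the range is about 2% to 13%. The highest cell in the table is 22%.

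**What a listing can and cannot show.** With 0 events in 8 treated hands, the one-sided 95% upper limit is 1 − 0.05^(1/8) = 0.312. A sign test on discordant pairs all in one direction gives 2 × 0.5⁵ = 0.0625 for five pairs and 2 × 0.5⁶ = 0.031 for six. A formal test at 8 subjects is therefore of little use, and the listing should be descriptive.

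**How much the *and* matters.** With no true effect, paired tests at 8 subjects and outcome correlation from 0 to 0.9, a benefit rule needing all five outcomes fires with probability about 0 to 0.007. One needing any single outcome fires with about 0.12 to 0.05. With an assumed d of 1.04 on every outcome and independent t-tests, the probabilities at correlation 0, 0.5 and 0.9 are 0.03, 0.15 and 0.34 for all five, and 0.97, 0.84 and 0.65 for any one. These are two very different rules.

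**The case against.** The best defence is that this is a single-site trial of 16 subjects in which section 24.3 lets investigators see everything, so a cluster of events would be noticed. That disposes of one tempting inference, that adverse reactions go unmonitored or can be seen only one case at a time. What stands is narrower: access is not a review step, and nothing directs anyone to compare hands.

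It may also be said that follow-up covers weakness well. A reader might infer that a review using 3-month data would come too late, since the "3-month (+/- 15 days) Follow-up" window opens at 90 − 15 = day 75 and six weeks is day 42. The documents do not support that. Section 14.1 says that weakness may last six weeks and gives no maximum, section 12.1 names no visit, and weekly reports run through the first three months.

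The simulation sets the power of a test against a listing that is only as complete as event reporting. That is fair. The percentages show that QuickDASH is unreliable for this purpose, not that a listing would capture every event.

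On blinding, a reader might infer that the principal investigator is unblinded. Section 12.1 does not say who runs the comparison, and the red and blue syringe labels in section 9.2 make a coded review possible. The supportable statement is that no coded review or firewall is described. An aggregate result would in any case not reveal which hand of a later subject was treated.

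A reader might also conclude that the benefit stop needs an alpha adjustment. Under the all-five reading, which the contrast with the harm rule suggests, false stops stay below 1% and no adjustment is needed.

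**Conclusion.** The main point holds: section 12.1 promises a review of harms, yet its list omits the protocol's safety endpoint, and no other section supplies a cumulative or by-hand review. This follows from the text alone and rests on no simulation. The 2% to 13% figure only answers the suggestion that QuickDASH would cover the gap; it assumes per-hand scoring, normal data, a 1 SD worsening in 3 of 8 treated hands and between-hand correlation from 0 to 0.7. The absence of a described firewall is secondary and carries modest risk. The *and* in the benefit rule calls for clarification only. This is an inexpensive improvement to safety oversight that should be made. It does not show that the trial's results would be invalid.

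**What to change.** - **Main change.** Add cumulative adverse events from the existing Adverse Event Form to the halfway review in section 12.1, as a descriptive listing: local events by hand, systemic events (such as allergy) overall. State that it is descriptive and that no events in 8 treated hands would not exclude a common event. Handling of individual events and the harm threshold stay as the sponsor has set them.
- **Blinding.** Have the statistician run the by-arm comparison and report only continue or suspend, or carry out the review under the red/blue code. Reconcile this with section 24.3, which now gives every investigator all data.
- **Benefit rule.** Write *all* if all five outcomes are meant.

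The cost is mainly protocol wording, since the form and the statistician are already in place. There are two real downsides. The principal investigator would no longer see by-arm results, and someone must be named to read the by-hand listing, possibly a clinician outside the study team.

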11.0 Data Management* and Confidentiality

11.1 The data will be analyzed for significant differences with aid of a statistician. A significance level of 0.05 will be used for statistical hypothesis testing. The results of the data analysis will be graphed for each parameter.

- Categorical variables, such as sex (male and female), age, and comorbidities (e.g., scleroderma) will be reported descriptively, as frequencies and percentages. Outcomes in this study are visual analog scale for pain (VAS Pain), Raynaud's Condition Score (RCS), and the Disabilities of the Arm, Shoulder and Hand Score (QuickDASH), which are continuous variables. In addition, the number of digital ulcers and number of attacks/episodes per week, which are discrete variables, will be measured as outcomes. These continuous and discrete variables will be expressed as mean \pm standard deviation, with standard error of the mean (SEM).
- To assess between group differences, an Independent samples t-tests will be conducted separately for the three time periods: baseline, 1-month, and 3-month. Additionally, a dependent sample t-test will be used to assess within-group differences from 1-month to 3-month, separately for the experimental and control groups. It is possible to use the baseline measurement as a covariate in an analysis of covariance (ANCOVA) and/or in a repeated measures ANOVA. Thus, the researchers will also explore these additional analyses if the sample size permits.
- All tests will be two-sided, and p-values < 0.05 will be considered statistically significant. Statistical analyses will be conducted using SPSS 24.0 (IBM; Chicago, IL).

PROTOCOL TITLE: The Effect of Abobotulinum Toxin A on the Symptoms of Raynaud's Phenomenon, a Double-Blind Randomized Placebo-Controlled Trial

11.2 Utilizing the statistical software G*Power it was determined that 16 patients would be needed to detect a 2-point difference in the RCS among the treatment arms. (G*Power) This assumes a standard deviation of 1.92, power of 0.8, alpha of 0.05, and effect size (d) of 1.04. (Merkel)

11.3 Data will be managed as follows:

- Data will be stored in the secure HIPAA-compliant database called REDCap.
- Unique identifiers will be created using sequential numbers (i.e. 1, 2, 4 etc.).
- No data collection instrument in REDCap will contain identifying information

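### The suspension rules in 12.1 test the change in each outcome, while 11.1 commits only to tests of visit values, so a halfway signal can be significant on one quantity and not on the other

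*Combined protocol and SAP*

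**What the plan says.** Section 12.1 sets a review after 8 subjects, with two rules for suspending the study.

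- The harm rule opens "If any of the change in VAS Pain scores, RCS, QuickDASH, number of digital ulcers, or number of attacks/episodes per week" and continues "for the treatment should become statistically significantly worse than the control with a" p-value below 0.05. One outcome is enough.
- The benefit rule opens "Alternatively, if the change in VAS Pain scores, RCS, QuickDASH, number of digital ulcers and number of attacks/episodes per week". It uses the same threshold but joins the five outcomes with *and*.

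Neither rule says what the change is measured from, at which visit, or with which test.

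Section 11.1 describes the between-group analysis differently: "an Independent samples t-tests will be conducted separately for the three time periods: baseline, 1-month, and 3-month". Since baseline is one of the tested periods, these are tests of visit values. The one change-type test it commits to is neither between hands nor from baseline: "a dependent sample t-test will be used to assess within-group differences from 1-month to 3-month, separately for the experimental and control groups". ANCOVA with baseline as covariate and repeated-measures ANOVA are mentioned, but only conditionally: "the researchers will also explore these additional analyses if the sample size permits".

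No section defines a between-hand test of change.

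**The concern.** The quantity that can halt the trial is one that the analysis plan never commits to testing. A chance difference between the toxin and saline hands at baseline moves the two quantities in opposite directions. If the toxin hands happen to start worse, their follow-up values tend to look worse while their changes look better. With 8 subjects such differences are not negligible.

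Two things are at stake. A suspension could rest on a result that 11.1's test, applied to the same subjects, would call not significant. And a harm that 11.1's test would detect could fail to meet the harm rule. The second matters more, because the rule exists to protect subjects.

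**Working it through.** **Inputs from the documents.** RCS difference 2 points, SD 1.92, d = 1.04, power 0.8, alpha 0.05 and 16 patients (11.2); two-sided tests (11.1); review at 8 subjects (12.1); one hand per arm within each patient (9.1).

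**Assumed, because the documents give no values.** SD 1.92 at both visits; baseline-to-follow-up correlation r = 0.3, 0.5, 0.7; between-hand correlation h = 0 to 0.7. Change is taken as change from baseline.

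**The plan's own figure.** d = 2/1.92 = 1.04. An exact two-sided independent t-test needs 15.5, so 16 per arm, with power 0.812. The stated 16 is reproduced as an independent-samples calculation in which each patient supplies one hand to each arm.

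**Smallest significant RCS difference at 8 subjects (independent t-test, 14 df, critical t = 2.145).**
- Visit values: SE = 1.92 × √(2/8) = 0.96, so 2.145 × 0.96 = 2.06 points.
- Change: SD = 1.92 × √(2(1 − r)) = 2.27, 1.92, 1.49 for r = 0.3, 0.5, 0.7. Half of this is the SE, so the thresholds are 2.44, 2.06 and 1.59 points.

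**Effect of chance imbalance.** The baseline difference between hands has SD 1.92 × √(2(1 − h)/8), which is 0.96, 0.68 and 0.53 for h = 0, 0.5 and 0.7. A baseline difference D shifts the expected follow-up difference by rD and the difference in change by −(1 − r)D. With r = 0.5 and D = 0.68 these are +0.34 and −0.34.

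**Two worked cases (r = 0.5, SE 0.96 for both quantities).**
- Toxin hands 1.0 point better at baseline and 1.5 worse at follow-up. Visit values: t = 1.5/0.96 = 1.56, p = 0.14. Change: t = 2.5/0.96 = 2.60, p = 0.021. The harm rule is met; 11.1's test is not significant.
- Toxin hands 1.0 worse at baseline and 2.5 worse at follow-up. Visit values: p = 0.021. Change: 1.5 points, p = 0.14. The harm rule is silent; 11.1's test is significant.

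**Simulation.** 8 subjects, true 2-point effect, both independent t-tests on the same data, 100,000 trials per setting. Ranges run over h = 0 to 0.7.

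| r | Visit values significant | Change significant | Of significant changes, visit values not | Of significant visit values, change not |
|---|---|---|---|---|
| 0.3 | about 50% | 33–38% | 27% | 45–53% |
| 0.5 | about 50% | 49–51% | 35–37% | 35–37% |
| 0.7 | about 50% | 71–80% | 44–45% | 14–20% |

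Significance in opposite directions occurred in at most 2 of 100,000 trials in any setting. The effect may be read as benefit or, by symmetry, as harm.

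**Candidate common quantity.** Power for a 2-point effect at 8 subjects, h = 0.5, all tests within patient:

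| r | Visit-value difference | Difference in change | Baseline-adjusted difference |
|---|---|---|---|
| 0.3 | 72% | 57% | 67% |
| 0.5 | 72% | 71% | 75% |
| 0.7 | 72% | 90% | 88% |

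The one-direction error rate is about 2.5% for all three. At 16 subjects and h = 0.5 the adjusted test has 97% to more than 99% power, against 89% for 11.1's independent test.

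**The case against.** The case against is substantial, and much of it stands.

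- Section 12.1 does not say *from baseline*. That is an inference, and the more basic gap is that reference, visit and test are all undefined. This stands, and it strengthens the case for rewriting 12.1.
- At 8 subjects 11.1's test has about 49% power, so it is non-significant in about half of all such looks. A disagreement rate of 27% to 45% is below that, so much of it reflects low power. This stands. It does not explain the second worked case, where visit values are significant and the change is not.
- A monitoring quantity need not equal the final one. That is true in general, but here both sections use the same outcomes and threshold, and no reason is given for the difference.
- Section 11.1 does foresee baseline-adjusted analysis. It is conditional and exploratory, so it does not close the gap.

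Three stronger readings are tempting, and the documents do not support them. A reader might infer that a trial stopped for benefit would then publish a contradictory result. Section 12.1 says only that the study is suspended, no section says that the 8 subjects would be reported under 11.1, and the two tests practically never reached significance in opposite directions. A reader might apply the 27% to 45% to a benefit suspension. Read literally, that rule needs all five outcomes, so RCS alone cannot trigger it. And a reader might conclude that change scores are always the weaker choice. At r = 0.7 the change score is the more powerful of the two quantities.

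**Conclusion.** The mismatch is in the text and needs no assumed value: 12.1 acts on changes, 11.1 commits to visit values, and the two have different rejection regions. Its size rests on correlations that the documents do not give and on reading change as change from baseline. Within the range examined, disagreement between significant and not significant is common in both directions, but partly because 8 subjects give little power. The figures are for a single outcome and so bear on the harm rule, where any one outcome suffices. The point is one of consistency and definition. Severity is low to moderate.

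**What to change.** In 12.1 and 11.1, name one between-hand quantity, one visit and one test for every outcome recorded per hand. A suitable wording: *the within-patient toxin-minus-saline difference at the stated visit, adjusted by linear regression for the baseline toxin-minus-saline difference*. Use it for both the halfway review and the final comparison, and state that change is not tested separately.

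Section 9.4 does not say which outcomes are recorded for each hand. Any outcome scored per patient cannot enter a between-hand rule in either section, so the list in 12.1 should be checked against the case report forms.

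**Cost.** A few sentences and no new data, since baseline is already collected. It does replace 11.1's independent test with a within-patient one, so 11.2 should note that its 16 was derived on an independent-samples basis. The adjustment uses one degree of freedom. At 8 subjects and h = 0.5, power is about 2 points below the change score at r = 0.7 (88% against 90%) and about 5 points below an unadjusted within-patient test at r = 0.3 (67% against 72%). It is above the change score at r = 0.3 and 0.5. The unfavourable case is uncorrelated hands with r = 0.3, where the same simulation gives 40% at 8 subjects against 49% for 11.1's test.

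A smaller remedy is to keep 11.1 as it is and reword 12.1 to use 11.1's test at a stated visit. That removes the mismatch but leaves both sections exposed to chance baseline imbalance.

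### The halfway benefit rule in 12.1 suspends the study at 8 subjects on an unadjusted p<0.05, and under the planned test a stop there selects an overstated effect in the outcome that crosses

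*Combined protocol and SAP*

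**What the plan says.** Section 12.1 sets one review at the halfway point of 8 subjects: "The principal investigator and statistician will review cumulative VAS Pain scores, RCS data, QuickDASH", digital ulcers and weekly attacks. Two rules follow.

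- Harm: "If any of the change in VAS Pain scores, RCS, QuickDASH, number of digital ulcers, or number of attacks/episodes per week for the treatment" is significantly worse at p<0.05, the study is suspended.
- Benefit: "Alternatively, if the change in VAS Pain scores, RCS, QuickDASH, number of digital ulcers and number of attacks/episodes per week for the treatment" is "statistically significantly better than the control with a $p < 0.05$ then the study will also be suspended immediately".

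The harm rule joins the outcomes with any/or, the benefit rule with and. Section 12.1 names no visit and no test, speaks of change, and does not define suspension.

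For the analysis, section 11.1 states: "A significance level of 0.05 will be used for statistical hypothesis testing". Tests are two-sided, and for the arms "an Independent samples t-tests will be conducted separately for the three time periods: baseline, 1-month, and 3-month". Section 11.2 says "16 patients would be needed to detect a 2-point difference in the RCS among the treatment arms" and adds: "This assumes a standard deviation of 1.92, power of 0.8, alpha of 0.05, and effect size (d) of 1.04". No interim boundary, reduced final level or bias-adjusted estimate appears.

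**The concern.** Eight subjects are half the planned information. A rule that stops on nominal significance there keeps the trials in which chance has pushed the difference up. It may also give a second chance of a false positive, because the same 0.05 is used at both looks.

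What is at stake is the reported estimate. Section 2.3 hopes that positive findings will help justify insurance coverage, and that preliminary findings could support further studies towards a new indication. An effect size taken from a stop at 8 subjects would be too large and imprecise for either use.

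**Working it through.** **Inputs.** From 11.2: difference 2 points, SD 1.92, d = 2/1.92 = 1.04, power 0.8, 16 patients. From 11.1: two-sided 0.05, independent t-test. From 9.1: each patient gives one treated and one control hand, so 8 patients are 8 hands per arm. Assumed, because the documents do not give them: between-hand correlation 0 to 0.8, between-outcome correlation 0 to 0.8, normal outcomes, and SD 1.92 for the variable tested at both looks.

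**The plan's own figure.** An independent two-sided t-test with d = 1.04 has power 0.785 at 15 per arm and 0.812 at 16. The stated 16 therefore reproduces as 16 hands per arm. A paired test with d = 1.04 for the between-hand difference would need 10. So 1.92 is taken as the per-arm SD.

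**Difference needed at the halfway look** (observed SD equal to 1.92): t(0.975, 14 df) × SD × √(2/8) = 2.145 × 1.92 × 0.5 = 2.06 points, above the planned 2. Power there is about 0.49. The same expression is the 95% CI half-width at 8. At 16 it is 2.042 × 1.92 × √(2/16) = 1.39.

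**Overstatement** = mean observed difference among trials that cross for benefit, divided by the true planned difference (simulation, one outcome, true d = 1.04):

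| Between-hand correlation | Stop at 8, independent test | Significant at 16 only, independent test | Stop at 8, paired test | Average over all trials, stopped or not, independent test |
|---|---|---|---|---|
| 0 | 1.36 | 1.11 | 1.37 | 1.09 |
| 0.5 | 1.23 | 1.05 | 1.14 | 1.06 |
| 0.8 | 1.11 | 1.01 | 1.01 | 1.03 |

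If all five outcomes must cross, the independent test gives about 1.1 to 1.5 times. That stop occurs in about 3% to 27% of trials, and only if every outcome, ulcers included, has d = 1.04.

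**False-positive error, all-five reading.** With no effect the stop fires in at most about 0.3% of trials. Overall error moves from 5.0% to at most 5.6%, the maximum coming from a wider check with between-outcome correlation up to 0.9.

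**False-positive error, per-outcome reading, one outcome, two looks.**

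- Paired test: 8.5% two-sided at any between-hand correlation. In the benefit direction, 4.3% against 2.5% for a single final test.
- Independent test, two-sided: 8.4%, 5.3%, 4.6%, 3.9% and 1.7% at between-hand correlation 0, 0.2, 0.25, 0.3 and 0.5. It crosses 5% at about 0.22. A final test alone gives 5.0%, 2.1% and 0.8% at 0, 0.3 and 0.5.

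**If subjects already injected are followed and analysed.** With 16 injected evenly over 8 months, the eighth is injected at month 4 and reaches 3 months at month 7, when 14 have been injected. At correlation 0 the estimate is then (8 × 1.36 + 6 × 1)/14 = 1.21 times the truth, and the half-width is about 1.49 points.

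**Subjects spared by a stop.** Over 8 months of recruitment: 16 − 10 = 6 on 1-month data and 16 − 14 = 2 on 3-month data. Over 10 months: 16 − 9.6 = 6.4 and 16 − 12.8 = 3.2.

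**The case against.** The strongest reply is that the rule rarely matters. The contrast between any/or and and makes all five outcomes the natural benefit reading, and on it error is essentially unchanged. The 3% to 27% firing rate also assumes a full effect on digital ulcers, although eligibility in 3.2 requires only a Raynaud's diagnosis. This stands: the upper end of the 1.1 to 1.5 range describes an uncommon event.

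Second, any significant result in a small trial is overstated, and the average over all trials is only 1.09 to 1.03. This also stands. The excess due to 12.1 is the step from 1.11–1.01 to 1.36–1.11 in the trials that stop.

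Third, the range is not universal. Read per outcome, if another outcome triggers the stop, RCS itself is overstated only 1.01 to 1.24 times. If 1.92 is the SD of the raw score rather than of the change, an assumed baseline-to-follow-up correlation of 0.3 to 0.7 gives 1.54 down to 1.03. These limits are accepted.

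Fourth, section 12 is safety monitoring. It says suspended, and nothing in it plans to declare efficacy. The harm therefore depends on the suspended data being reported as the result. But 12.1 gives no rule for resuming and does not say how such data would be analysed, so nothing prevents that.

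**Conclusion.** The point holds in limited form. As written, 12.1 can end the study on a selected estimate from 8 subjects. With 11.1's test, the outcome that crosses is overstated about 1.36 to 1.11 times (one outcome) or about 1.1 to 1.5 times (all five), for assumed between-hand correlation 0 to 0.8. A paired test gives 1.37 to 1.01 for one outcome. Overstatement and imprecision are smaller if subjects already injected are followed and analysed.

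A reader might infer three stronger conclusions that the documents do not support:

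- **That the rule inflates false-positive error outright.** This needs the per-outcome reading, and then either a paired test, which 11.1 does not name for comparing arms, or a between-hand correlation below about 0.22 for the total to exceed 5%.
- **That the trial will claim efficacy at 8 subjects.** Section 12.1 only suspends.
- **That the principal investigator is unblinded by the review.** Judging better or worse requires someone to hold the code, and 12.1 states no masking. But the documents do not say that arm-labelled data are shown, and the red and blue syringe labels in 9.2 would allow a coded comparison.

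This should be fixed. Confidence is medium, because the test, the visit and the between-hand correlation are not given.

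**What to change.** **Recommended.** In 12.1, delete the benefit bullet and state that the study will not be suspended for benefit at the halfway review. The final 0.05 then needs no adjustment for a benefit look.

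**Alternative.** Restrict the rule to the RCS between-hand difference at one named visit, by paired t-test at two-sided p<0.001. Change the final RCS comparison in 11.1 to a paired t-test at 0.05. Benefit-direction error is then about 2.5%. State whether change or value is tested, and what suspension means for follow-up and the final analysis. This controls error but not overstatement. When the between-hand difference is 1.04 of its own SD, the rarer stop overstates 1.38 times, against 1.14 at p<0.05, so deletion is preferable.

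**In either case.** As a precaution, have the statistician alone see any halfway efficacy comparison by arm. Adverse events, and unblinding where safety requires it, stay available to the clinician responsible. The harm trigger is left to the sponsor's safety judgement. If its crossings are counted, two-sided paired error is 6.8% after either change, against 8.5% now.

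**Cost.** Deletion changes wording in 12.1 only; the alternative also changes 11.1. Someone other than the principal investigator must hold the colour code. Early stopping for benefit disappears or becomes rare: at p<0.001, paired, d = 1.04, it fires in about 3%, 9%, 21% and 38% of trials at between-hand correlation 0, 0.5, 0.7 and 0.8. What is forgone is sparing about 6 of 16 subjects on 1-month data, or 2 to 3 on 3-month data.
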